Confocal microscopy will be conducted daily to collect 3D image data of the cells and track their position and behaviour over time. At the end of the assay, the 3D cell cultures will be fixed or snap-frozen for further 3D immunofluorescence analyses or used for embedding, sectioning and assessment of spatial proteomics. For targeted therapies, RNAseq, IF and proteomics data will be integrated to confirm drug MoA and identify other potential therapeutic targets. Concurrently, 3D image data will be processed through a computer vision pipeline to measure functional metrics of the *ex vivo* 3D cell cultures, including cell viability, tumour culture width and cell migration, both at a bulk tumour level and at a single-cell resolution. A patient report is generated outlining an individual patient sample's response to each therapy tested.

**Potential additional analyses:**

- DNA analyses:
  - Tumour mutational burden (TMB)
  - Microsatellite instability (MSI)
  - Fluorescent in-situ hybridisation (FISH)
  - Genome-wide methylation patterns
  - Whole genome sequencing
  - Whole exome sequencing
  
- RNA analyses:
  - RNASeq
  - Microarrays
  - Quantitative reverse transcription PCR (RT-qPCR)
  - Spatial analyses (Nanostring, ResolveBiosciences)
  
- Protein analyses:
  - Flow cytometry (FC)
  - Immunofluorescence (IF)
  - Analysis of secreted factors

**Figure 2: PEAR-GLIO laboratory workflow.** (1) Patient gives a pre-op blood sample (2) Patient undergoes surgery as part of standard of care (3) Viable cells are isolated from the tumour and immune cells are isolated from blood samples (4) Tumour-dissociated cells and immune cells are stained with live-cell and dead-cell fluorescent dyes. (5) The cells are cultured simultaneously in multiple Pear Bio hydrogels contained in a microfluidics device. (6) Standard-of-care chemotherapy and targeted treatments are dosed within the device whilst (7) daily imaging allows for live tracking of cell viability and migration. (8) Wherever additional cells are available, omics assays (e.g. RNA sequencing and immunofluorescence) will be run in parallel to check expression of common biomarkers and validate drug mode of action. (9) Computer vision (CV) is implemented to detect changes in cell morphology, viability, and position (amongst other parameters) over time in order to make an informed prediction of differential treatment efficacies.

### 3.5 Patient evaluability

In order to be considered evaluable, patients must meet the eligibility criteria, consent to the use of their surgical sample and blood for the study, and yield a research sample with sufficient weight and tumour cell content resulting in the establishment of a successful cell culture in the Pear Bio laboratory.

### 3.6 Replacement of patients

Patients who do not meet the evaluability criteria set out in section 3.5 will be replaced.

### 3.7 Target accrual

A maximum of 50 evaluable patients will be recruited in this study. On recruitment of the first 10 patients, the Trial Management Group (TMG) will meet to assess whether monthly recruitment targets are met, and to confirm sample quality and successful culture rates upon processing at the Pear Bio laboratory.

The TMG will use the results to determine whether to increase accrual up to a maximum of 50 patients.

## 4: PATIENT SELECTION

### 4.1 Inclusion criteria

1. Patient diagnosed with operable brain tumour, thought likely to be primary solid brain tumour on imaging (grade 2 - 3 meningioma or grade 1 - 4 for other tumours) or with histologically proven primary malignant solid brain tumour and due to undergo surgery as clinically indicated
2. Able to give written informed consent prior to admission to this study;
3. Female or male aged  $\geq 18$  years;
4. Patient consents to the use of their surgical sample and 40mL of whole blood for research purposes;
5. Surgical sample yields  $\geq 0.4$ g for the study;
6. Patient consents to providing histopathology data (e.g., confirmation of histological subtype as oligodendroglioma) and other pseudonymised health information including imaging, treatment and outcome data.

#### **4.2 Exclusion criteria**

1. Inoperable or biopsy only
2. Suspected lymphoma or myeloma, or grade 1 meningioma;
3. Preoperative haemoglobin levels below 120g/L;
4. Patients who have already received chemotherapy, targeted therapy, immunotherapy, or radiotherapy less than 30 days before date of surgery, unless delivered as part of a clinical trial (must be discussed with sponsor on a per-patient basis)
5. Recurrence of cancer originating from a site other than the brain;
6. Any other disease, metabolic dysfunction, physical examination finding, or clinical laboratory finding that, in the investigator's opinion, gives reasonable suspicion of a disease or condition that may affect the interpretation of the results, render the patient at high risk from treatment complications or interferes with obtaining informed consent.

## **5: STUDY PROCEDURES AND SCHEDULE OF ASSESSMENTS**

### **5.1 Patient identification**

Patients will be identified in multi-disciplinary team meetings or in outpatient clinics by their clinical care team.

Only individuals with legitimate access to medical records (such as the patient's clinical care team) will be accessing these records for the purpose of identifying participants.

## 5.2 Informed consent procedure

It is the responsibility of the Investigator, or a medically trained person delegated by the Investigator to obtain written informed consent from each subject **prior** to participation in this study, following adequate explanation of the aims, methods, anticipated benefits and potential hazards of taking part in the study. Ample time must be given for consideration by the patient before taking part. Attempts will be made to arrange for an official hospital translator for any participant who is not competent or comfortable with communication in English. The translator will be asked to read through the Patient Information Sheet (PIS) and Consent Form and to translate each section for the participant. Written informed consent will only be obtained from those who the Investigator feels assured have understood the implications of participation in the study. Patients with mental capacity issues will not be included in this study. The PI must document in the patient's notes when the PIS was given to the patient and when informed consent was obtained.

If new safety information becomes available, the CI, in conjunction with the TMG, will review the study, update the PIS accordingly and resubmit for relevant approvals. The CI will review the new safety information and assess whether an urgent TMG meeting should be convened or whether this information can be reviewed at the next scheduled meeting. All patients, including those already undergoing scans, should be informed of the new information, given a copy of the revised PIS, and asked to give their consent to continue in the study. Patients will not be re-consented following amendments that do not affect safety or the number of assessments/visits required.

## 5.3 Patient enrolment

Principal Investigator(s) (PIs) at each recruiting site must keep a record of all patients screened for entry into this study, including those deemed ineligible after screening. Copies of the screening logs should be filed in the Investigator Site File (ISF). For each patient, the primary reason for exclusion should be recorded. Diagnostic data obtained as part of the patient's standard care can be used to determine eligibility provided they fall within the protocol defined timelines. Written informed consent must be obtained prior to the patient undergoing any study-specific procedures.

After ensuring that a patient has consented to participate in the study, a registration electronic case report form (eCRF) must be completed. Patients will then undergo screening to confirm study eligibility. Once it has been confirmed that a patient meets all eligibility criteria, the study site will submit the patient's eligibility information to the coordinating centre. The clinical site will assign patients with a unique study ID for use in all correspondences (the Sponsor will provide a sequence of codes to assign). To ensure patient confidentiality, patients will only be identified using their assigned study ID on eCRFs, other study specific forms and all communications to the Sponsor. It is the PI's responsibility to maintain a confidential record of the identity (i.e., full name, date of birth and hospital number) for the patients enrolled in this study and their assigned study ID. At the end of the study, this record should be archived along with the ISF.

Full details of how to enrol a patient via the PEAR-GLIO eCRF can be found in the eCRF completion guidance document.

#### 5.4 Schedule of assessments

Patients may not need to make any additional site visits as the samples collected for the study can be taken from standard of care procedures. Due to logistical reasons, it may be difficult for the recruiting site to carry out all screening assessments in one day. Patients will be fully informed about the number of visits required to confirm eligibility in the trial. Subsequent visits will be as per standard of care at the local institution. For a summary of assessments see Table 1.

	Baseline (Before surgery)	At or shortly after surgery	Standard of care follow-ups	If cancer recurs
Informed consent and eligibility checks	B			
Demographics and medical history	A			
Height, weight ECOG	A			
Concomitant medication	A			
Results from standard of care haematology, biochemistry assessments	A			
Standard of care imaging	A			
Tumour size evaluation	A			
Standard of care surgery		A		
Histopathology 		A		A
Collection of blood for the study 		B (40mL whole blood)		
Collection of tissue and data for the study 		B		

Transfer of data for the study 		B	B	B
Adverse Events by CTCAE v5.0 		B		
Treatment and follow-up as clinically indicated			A	
Follow-up assessments for recurrence 			A	
Further therapy 				A
A = Standard of care assessment B = Study-specific assessment or data collection				

**Table 1: Schedule of assessments**

Table notes:

1. A redacted histopathology report will be sent to Pear Bio when it is ready (i.e., it does not have to be sent alongside the tissue, blood and other available data from the day of the surgery).
2. Available data is transferred alongside the tumour sample within 24 hours of surgery to Pear Bio's laboratory. Any remaining data will be transferred as soon as feasible, and we will transfer any further imaging at a single timepoint at 12 months after surgery
3. Relating only to research procedures (e.g., taking a volume of blood that is beyond standard care for a given patient). This can be conducted by telephone – physical examination to be done only if clinically indicated.
4. Collected only if available for consenting patients within the study period.
5. Collected only if available for consenting patients within the study period.

## 5.5 Procedures and measurements

### 5.5.1 Demographics and medical history

Demographic data collected will include age, sex and race/ethnicity. Details of medical history obtained as part of standard of care will be collected, including details of any relevant medical conditions occurring prior to consent.

Details will also be collected on the patient's cancer diagnosis, including site, date of diagnosis, and tumour size.

### 5.5.2 Height, weight and performance status

Baseline height (cm) and weight (kg) will be collected from the medical records.

Performance status data will be collected at baseline using the ECOG performance score according to Table 2. This information will be recorded in the e-CRF.

Grade	ECOG
0	Fully active, able to carry on all pre-disease performance without restriction
1	Restricted in physically strenuous activity but ambulatory and able to carry out work of a light or sedentary nature, e.g., light house work, office work
2	Ambulatory and capable of all self-care but unable to carry out any work activities. Up and about more than 50% of waking hours
3	Capable of only limited self-care, confined to bed or chair more than 50% of waking hours
4	Completely disabled. Cannot carry on any self-care. Totally confined to bed or chair
5	Dead

**Table 2: ECOG performance status**

### **5.5.3 Concomitant medication**

All medications (including prescription medications and over the counter preparations) taken by the patient during the screening period will be documented as concomitant medications. The following details will be collected at baseline: drug name, reason for treatment, dose/units, route of administration, frequency.

### **5.5.4 Haematology and clinical biochemistry**

The results of any standard of care haematology and clinical biochemistry tests will be collected at baseline. The date and result for each test must be recorded in the appropriate eCRF.

### **5.5.5 Treatment details**

Patients will receive surgery as per standard of care. Consenting patients will have a portion of their tumour and blood used for this study.

For patients who have adjuvant therapy within the study period, the following details will be collected at each cycle: drug name, start date and end date, dose/units, dose reductions/interruptions, reasons for any treatment changes/interruptions/dose reductions, or details of radiotherapy dose, fractionation, start and end dates, and for surgery, dates and times of surgery and post-operative stay.

### **5.5.6 Tumour size evaluation**

PEAR-GLIO Protocol v1.0  
3rd March 2023

Measurements will be made by contrast-enhanced MRI. Imaging reports and pseudonymised images will be included as study data collected and transferred to Pear Bio, provided the imaging was done within the period of 3 months prior to surgery or during the follow-up period. Sites will transfer initial imaging shortly after surgery, and again at a single timepoint 12 months after surgery.

#### **5.5.7 Adverse events**

Adverse events will be restricted to those resulting from study-related procedures (e.g., a volume of blood collected beyond standard care to satisfy study requirements). The following details will be collected: AE term, date of onset, date of resolution, CTCAE grade (maximum intensity), seriousness, investigator causality rating against research procedures (yes or no), action taken with regard to the research procedures and outcome.

#### **5.5.8 Surgical biopsy and blood collection**

40mL of whole blood will be collected in 4x 10mL EDTA tubes on the day of surgery.

At the time of surgery, a portion of the tumour resected from surgery will be provided to Pear Bio ( $\geq 0.4\text{g}$ ). Samples must be placed in tissue transport medium to be supplied by Pear Bio.

Each sample should be stored at 4°C before being transported by express courier to Pear Bio so that samples arrive within 24 hours of collection; blood and tumour samples may be sent separately because they may be collected up to 4 days apart.

#### **5.5.9 Exposure to ionizing radiation**

There are no expected research exposures to ionising radiation. Although patients may undergo imaging with ionising radiation, and many may undergo radiotherapy, all of these will be delivered as part of routine care, and not as part of the trial. In addition, disease assessments are routinely carried out using MRI, which is a non-ionising modality.

### **5.6 Exploratory research**

All patients will be consented for the collection and use of their tumour tissue and blood samples. All samples will be link-anonymised and only identified by the study ID and unique sample number allocated by the clinical site (Sponsor to provide sequence of codes to assign). These results may be reported separately from the clinical study report.

#### **5.6.1 Chain of custody of biological samples**

In all cases, patients will be consented for the collection and use of their biological samples and a full chain of custody will be maintained for all samples throughout their lifecycle. The Investigator at each site is responsible for maintaining a record of full traceability of biological

samples collected from patients while these are in storage at the site; either until shipment or disposal. Any sample receiver (e.g., sub-contracted service provider) will keep full traceability of samples from receipt of arrival to further shipment or disposal (as appropriate).

In the event that a patient withdraws their consent from the study, all samples and data collected up to that date will be used in the study, but no further data will be collected. As the Sponsor, Ourotech Limited (trading as Pear Bio) will maintain oversight of the entire lifecycle through internal procedures and monitoring of the study site(s). The Sponsor will be the custodian of the samples. Samples will be transferred from the participating site to Ourotech Limited (trading as Pear Bio). At the end of the study, unused samples (or portions of samples) will be retained for future research while all used samples (or portions of samples) will be disposed of in accordance with the Human Tissue Act 2004.

### **5.7 Patient withdrawal**

Patients may voluntarily withdraw from the study at any time. Patients will also be withdrawn from the study if their research sample has insufficient weight (<0.4g) or tumour content (<100 000 viable cells), or the sample fails to establish a culture in the laboratory.

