## 2.2 Secondary objectives and endpoints

Secondary objectives	Endpoints

Assess the accuracy of Pear Bio's assay at correlating to patient progression free survival (PFS)
	
Tumour response will be measured as clinically indicated (typically every 3 months), and at all subsequent timepoints until disease progression, as per standard of care.
 
Disease progression is evaluated by the patient's radiologist and is defined by RANO guidelines.
 
Kaplan–Meier curves will be generated on the patient population, and where feasible, based on their line of treatment and for each therapeutic option (if n is sufficient). These curves will be compared to reported data to determine how representative the patient population is of past trials and clinical practice.
 
Computer vision biomarkers will be categorised into low/high groups to determine their correlation with PFS. This analysis will not demonstrate the patient benefit of using Pear Bio's tool, but it will generate hypotheses for interventional trials designed to demonstrate patient benefit.

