## **7: STATISTICAL CONSIDERATIONS**

### **7.1 Sample size**

A maximum of fifty (50) evaluable patients will be recruited to this study. This study is not formally powered due to the proof-of-concept nature of the study and broad inclusion criteria. However, the number of samples acquired in this study will enable Pear Bio to conduct analytical validation on the robustness of its precision medicine platform in brain cancer.

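### Withdrawing patients whose samples fail in the laboratory leaves a PFS cohort of culture successes, so the section 2.2 curves may not show how representative the recruited patients are

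*Combined protocol and SAP*

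**What the plan says.** Four rules decide who remains in the cohort.

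- **Evaluability (3.5).** The sample must have enough weight and tumour cells, "resulting in the establishment of a successful cell culture in the Pear Bio laboratory".
- **Withdrawal (5.7).** "Patients will also be withdrawn from the study if their research sample has insufficient weight (<0.4g) or tumour content" (fewer than 100,000 viable cells), "or the sample fails to establish a culture in the laboratory".
- **Replacement (3.6).** "Patients who do not meet the evaluability criteria set out in section 3.5 will be replaced".
- **Target (7.1).** "A maximum of fifty (50) evaluable patients will be recruited to this study".

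Section 2.2 plans Kaplan-Meier PFS curves on the patient population, without defining that population. It gives their purpose: "These curves will be compared to reported data to determine how representative the patient population is of past trials and clinical practice".

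Section 5.6.1 says that earlier data are kept and no more are collected, but it says so only for patients who withdraw consent. No section says what happens to outcome data after a sample-based withdrawal. Inclusion criterion 6 (4.1) asks every patient to agree to provide "other pseudonymised health information including imaging, treatment and outcome data".

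**The concern.** Sample adequacy and culture success become known only after surgery, when the patient is already recruited. Removing and replacing patients on that basis filters the cohort by tumour yield and by growth in the laboratory. If growth is related to prognosis, the PFS curve of the remaining patients differs from that of the patients recruited. A gap between the curve and published data could then come from recruitment or from the laboratory filter, and agreement could hide a difference in either.

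A relation is plausible. Under the heading on other primary brain tumours, section 1.2 gives two reasons for leaving out grade 1 meningioma: its outcomes are very good, and it is unlikely to grow in the platform. Whether anything similar holds among the grade 1 to 4 tumours that are admitted is unknown. Answering that needs outcomes for patients whose samples failed, and the plan does not provide for collecting them.

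Section 1.3 says the study data will inform the design of later trials, so a misread of representativeness could carry forward.

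**Working it through.** The plan states no figure to reproduce: 50 is a cap, with no power calculation behind it.

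**1. Who is left.** Under 3.5, 3.6, 5.7 and 7.1 the 50 patients counted are those with an established culture. Section 5.7 has three triggers, which differ. A sample under 0.4 g also fails inclusion criterion 5 ("Surgical sample yields" at least 0.4 g), so it is an eligibility failure as well. Too few viable cells and failed culture are not eligibility criteria, so they are the clearer selection.

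**2. How many are lost.** The documents give no success rate, so assume s = 50-90%. To reach 50 evaluable patients, the number enrolled is 50/s, rounded up.

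| s (assumed) | Enrolled | Not evaluable |
|---|---|---|
| 90% | 56 | 6 |
| 80% | 63 | 13 |
| 70% | 72 | 22 |
| 60% | 84 | 34 |
| 50% | 100 | 50 |

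**3. How far the curve could move.** Assume exponential PFS with median m months in successes (8 or 12) and a failure-to-success hazard ratio HR of 0.5 to 2.0. None of these values is in the documents.

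- Successes at 12 months: S1 = 0.5^(12/m)
- Failures at 12 months: S0 = 0.5^(12 × HR/m)
- All patients: s × S1 + (1 - s) × S0
- Difference, successes minus all: (1 - s) × (S1 - S0)

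Example with m = 8, s = 0.7 and HR = 2: S1 = 0.5^1.5 = 0.354 and S0 = 0.5^3 = 0.125. All patients: 0.7 × 0.354 + 0.3 × 0.125 = 0.285. The difference is +6.9 points.

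| m | HR | s = 50% | s = 70% | s = 90% |
|---|---|---|---|---|
| 8 | 0.5 | -12.1 | -7.2 | -2.4 |
| 8 | 1.0 | 0 | 0 | 0 |
| 8 | 2.0 | +11.4 | +6.9 | +2.3 |
| 12 | 0.5 | -10.4 | -6.2 | -2.1 |
| 12 | 1.0 | 0 | 0 | 0 |
| 12 | 2.0 | +12.5 | +7.5 | +2.5 |

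Entries are percentage points of 12-month PFS. The range is about -12 to +13.

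**4. Would keeping failures in the data set, but censored at withdrawal, help?** Sections 2.3 and 7.2.3 judge culture success on day 3, so censoring was set there. The simulation used 2,000 runs with 50 successes, 22 failures and m = 8. It gave these mean Kaplan-Meier estimates at 12 months:

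| HR | Successes only | Failures censored at day 3 | All followed |
|---|---|---|---|
| 2.0 | 35.2% | 35.1% | 28.3% |
| 0.5 | 35.3% | 35.3% | 42.7% |

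Censoring at day 3 gives almost the same curve as leaving the failures out. Only continued follow-up changes it.

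**5. Against sampling error.** With 50 patients, complete follow-up and 12-month PFS of 35.4%, the 95% half-width is 1.96 × √(0.354 × 0.646/50) = 0.133, or about 13 points. The largest shifts in step 3 are about as large as this; most are smaller.

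**The case against.** The strongest reply is that section 5.7 does not say outcome follow-up stops, and that the rule ending data collection in 5.6.1 concerns withdrawn consent. This stands. A reader might infer that failures are certainly not followed, but the documents only imply it through the word withdrawn. The silence needs resolving all the same, because sites could act either way.

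A second reply is that the patient population in 2.2 may simply mean the assayed cohort, and that comparing this cohort with published data is legitimate. It is, if labelled so. It then describes the assayed patients and cannot separate recruitment from the laboratory filter.

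Three stronger readings are tempting and not supported:

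- **That the selection is invisible.** Failures stay in the denominator of the culture success rate (2.3, 7.2.3). Table 1, note 2, has available data travel with the sample within 24 hours of surgery. The Trial Management Group reviews sample quality and culture rates after 10 patients (3.7, 7.3). Baseline features could therefore be compared now. What is at risk is later outcome and perhaps the histopathology report, which may follow later (Table 1, note 1).
- **That following failures would repair every outcome association.** Linking ex vivo response to PFS needs a culture by design.
- **That the bias has a known direction, such as too many high-grade tumours.** The remark on growth concerns an excluded tumour type. If success depended only on grade, the bias would vanish within grade. Section 2.2 plans curves by line of treatment and therapy, but only where numbers allow.

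The stakes are also modest. Section 1.1 rules out formal statistical analysis of patient outcomes, section 2.2 calls its biomarker analysis hypothesis-generating, and the primary analysis (7.2.1) uses no outcomes.

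**Conclusion.** The point holds in a limited form. The withdrawal, evaluability and replacement rules together leave a PFS cohort of culture successes, and no section keeps the others in outcome follow-up. If culture success is related to prognosis, the representativeness comparison in 2.2 does not describe the recruited population, and the plan has no means of finding out.

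Size and sign cannot be derived from the documents. The range of about -12 to +13 points rests wholly on the assumed success rates, hazard ratios, medians and exponential form, and it includes zero. Low-to-moderate priority.

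**What to change.** 1. In 5.7, for viable-cell and culture failures, replace withdrawal from the study with *not evaluable for the laboratory endpoints*. Continue routine outcome data transfer to 12 months where the consent form allows. Criterion 6 points that way, but the consent form was not available to this review and its wording must be checked.
2. In 2.2, define the Kaplan-Meier population. Draw the representativeness curve on all consented, operated patients with outcome data, flag those under 0.4 g, and show the evaluable-only curve beside it.
3. Add one descriptive table of baseline features and PFS for culture successes and failures.
4. Label ex vivo-to-outcome associations as limited to culture successes.

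Replacement under 3.6 and the primary laboratory analysis stay as they are. The cost is modest extra data transfer from sites, with no new procedures: about 6 more patients at 90% success, 22 at 70% and 50 at 50% (rates assumed). If the sponsor prefers evaluable patients only, the minimum is to label the curves so and report the number of withdrawals with reasons.
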